3.3.2 Exclusion criteria

Subjects who meet any of the following criteria are not eligible for this study:

- 1) Currently participating in other clinical studies, or less than 4 weeks after the end of treatment in the previous clinical study.
- 2) In the past 3 years, there has been a history of malignant tumors other than GBM, or other primary malignant tumors that have not been cured.
- 3) Previous history of brain radiation therapy.
- 4) Pregnant or lactating women.
- 5) After evaluation, there are patients with contraindications to radiotherapy.
- 6) Serious active comorbidities that may affect the treatment of this study.
- 7) Active infections that require systematic anti infective treatment, including but not limited to bacterial, fungal, or viral infections.
- 8) Patients with heart failure, unstable angina, severe uncontrolled ventricular arrhythmias, acute ischemia or myocardial infarction as determined by the New York Heart Association (NYHA) functional classification within the first 6 months of screening.
- 9) QTcF interval > 480 milliseconds, unless secondary to bundle branch block.
- 10) Suffering from uncontrollable comorbidities, including but not limited to uncontrolled hypertension, active peptic ulcers, or bleeding disorders.
- 11) Individuals with a history of mental illness in the past; Individuals without legal capacity or with limited legal capacity.
- 12) Medical history or disease evidence that may interfere with the trial results, hinder the subjects' full participation in the study, abnormal treatment or laboratory test values, or other situations that the researchers consider unsuitable for inclusion.

3.3.3 Discontinue research treatment

Subjects may discontinue treatment at any time for any reason, or at the discretion of the investigator in the event of any adverse event. In addition, if the subject is not suitable for treatment, violates the study protocol, or for management and/or other safety reasons, the researcher may discontinue the subject's treatment.

For any of the following reasons, subjects must discontinue treatment but may continue to be monitored during the study:

- The subject or the subject's legal representative requests to stop treatment.
- Adverse events that require discontinuation of treatment as specified in the protocol have occurred.
- Concurrent diseases that hinder further treatment occur.
- The researchers decided to withdraw the subjects from the study.
- The serum pregnancy test result of the subject is positive.
- Poor compliance of the subjects, failure to receive treatment on time, ineffective communication and coordination by the researchers, or possible significant deviations in the trial results that cannot be remedied.

- Researchers believe that based on the disease or personal condition of the subjects, continuing to provide study treatment would put them at unnecessary risk.
- Complete the treatment specified in the plan.

3.3.4 Follow up on withdrawn cases

If the subject or the subject's legal representative withdraws the informed consent form for participation in the study, the subject must withdraw from the study. If the subject withdraws from the study, they will no longer receive treatment or at planned visits. Subject to the subject's consent, participants can undergo survival follow-up after withdrawing from the study. If the subject is lost to follow-up, they must withdraw from the study. Any patient who withdraws from this study for reasons other than progression should continue to undergo imaging evaluation for a predetermined period of time to collect information about disease progression, until imaging disease progression occurs, new anti-tumor treatment begins, informed consent is withdrawn, death occurs, or the study ends (whichever occurs first). After recording disease progression, researchers need to call patients, their families, or their current treating physicians at least once a month to collect long-term follow-up information on survival.

4 , Sample size calculation

(1) Sample size estimation

The aim of this study is to evaluate the progression free survival (PFS) at 12 months in the experimental group receiving intensified adjuvant therapy in addition to the standard treatment Stupp regimen. Based on retrospective research and preliminary data from our center, it is estimated that the PFS of the Stupp group will be 40% and the experimental group will be 70%. To ensure the reliability of the research results, we set the alpha error to 0.05 and the beta error to 0.20 to ensure that the experiment has sufficient statistical power to detect differences between the two groups. Based on these parameters, it is calculated that each group requires 50 patients, for a total of 200 patients. Considering a 5% dropout rate, we plan to recruit 210 patients to ensure sufficient sample size for the final analysis.

(2) New Randomize Method

This project intends to use Bayesian adaptive randomization method to dynamically adjust the probability of patients being assigned to each treatment group. The specific implementation is as follows:

Initial randomization: Among the first 28 patients, an average of 7 were allocated to each group to ensure balance between the two groups during the initial stages of the trial.

Bayesian response randomization: Starting from the 29th patient, the 12-month PFS rate will be re estimated for every 16 patients enrolled, and subsequent randomization probabilities will be calculated based on observed data. This process will use Bayesian statistical principles

to dynamically adjust the probability of patient randomization by updating prior knowledge and new data, in order to improve trial efficiency. Randomization software: We will use professional randomization software, such as SAS or randomization packages in R language, to ensure the fairness and reproducibility of the randomization process.

5 , Data management and confidentiality

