3.1 Research overall design

This study is a prospective, randomized, controlled, open label, single center phase II study that uses Bayesian adaptive randomization to assess the efficacy and safety of intensified adjuvant therapy in newly diagnosed GBM patients undergoing partial surgical resection or short-term recurrence progression, based on the Stupp standard treatment regimen. Newly diagnosed GBM patients who undergo partial surgical resection or short-term recurrence progression (2-6 weeks after surgery before radiotherapy), after signing informed consent forms, will be screened to meet inclusion and exclusion criteria. In the first stage of Bayesian adaptive randomization, qualified subjects will be stratified and randomized in a 1:1:1:1 ratio to Stupp group, Stupp+PD-1/VEGF bispecific group, Stupp+PD-1/CTLA-4 bispecific group, and modified Stupp group with adjusted radiotherapy dose. In the second stage of Bayesian adaptive randomization, probability estimates are continuously updated based on the efficacy evaluation results of each group in the first stage, and the proportion of individuals randomized to each treatment group is dynamically

adjusted according to the trial results. A new round of randomization is conducted for each group of 16 individuals. The four treatment plans are as follows:

Stupp group: Synchronized TMZ radiotherapy and chemotherapy will begin 2-6 weeks after surgery, and 6 cycles of adjuvant TMZ chemotherapy will begin 28 days after completing the synchronized radiotherapy and chemotherapy. Radiotherapy regimen: PTV1 60Gy/30F in high-risk areas around the tumor bed, 54Gy/30F in low-risk areas. TMZ synchronous chemotherapy regimen: 75mg/m² po qd. TMZ adjuvant chemotherapy regimen: The first cycle is 150mg/m² po qd on d1-5,28 days; Cycle 2-6: Cycle 1: 200mg/m² po qd for d1-5,28 days.

Stupp+PD-1/VEGF dual antibody group: Starting 2-6 weeks after surgery, synchronous TMZ radiotherapy and chemotherapy will be performed. After completing synchronous radiotherapy and chemotherapy for 28 days, TMZ combined with PD-1/VEGF dual antibody will be used as adjuvant therapy. PD-1/VEGF dual antibody 20mg/kg intravenous infusion once, with a cycle of 21 days.

[figure not shown]

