Stupp+PD-1/CTLA-4 dual antibody group: Starting 2-6 weeks after surgery, synchronous TMZ radiotherapy and chemotherapy will be performed. After completing synchronous radiotherapy and chemotherapy for 28 days, TMZ combined with PD-1/CTLA-4 dual antibody will be used as adjuvant therapy. PD-1/CTLA-4 dual antibody 6mg/kg intravenous infusion once, with a cycle of 14 days.

Modified Stupp group: Starting 2-6 weeks after surgery, synchronous TMZ radiotherapy and chemotherapy will be performed. For partially resected lesions or short-term recurrence and progression lesions after surgery, high-dose PGT 66Gy/30Gy will be given locally. PTV1 in high-risk areas around the tumor bed will be 60Gy/30F, and in low-risk areas will be 54Gy/30F. After completing synchronous radiotherapy and chemotherapy for 28 days, 6 cycles of adjuvant TMZ chemotherapy will be started.

This study is divided into three stages: screening period, treatment period, and follow-up period. The screening period is 2-6 weeks after surgery. Treatment period: Subjects who meet the inclusion criteria but do not meet the exclusion criteria will receive postoperative intensive adjuvant therapy after signing the informed consent form. Follow up period: After stopping the study treatment, the subjects enter the follow-up period. Follow up period: Head MRI examination and evaluation will be conducted at baseline, postoperative, before radiotherapy, and after radiotherapy. MRI enhanced scans will be performed every month during the follow-up period to observe PFS until the end of the follow-up period. For subjects who have not withdrawn their informed consent form, survival information (i.e. date and cause of death, subsequent tumor treatment, etc.) will be collected every month through telephone and/or clinical visits.

This study is expected to have an enrollment period of 24 months and a follow-up period of 24 months.

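### The 50 patients per group and 80% power in Protocol section 4 belong to a fixed equal-allocation trial, not to the adaptive four-arm design that is planned

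*Protocol*

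**What the plan says.** Part (1) of Protocol section 4 sets out the planning assumptions for 12-month PFS: "it is estimated that the PFS of the Stupp group will be 40% and the experimental group will be 70" per cent, and "we set the alpha error to 0.05 and the beta error to 0.20". It speaks of a difference between two groups and concludes "Based on these parameters, it is calculated that each group requires 50 patients, for a total of 200 patients". A 5% dropout allowance takes the target to 210.

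Part (2) of the same section describes how patients will be allocated. Equal allocation covers only the start: "Among the first 28 patients, an average of 7 were allocated to each group". After that the plan is to "use Bayesian adaptive randomization method to dynamically adjust the probability of patients being assigned to each treatment group", and "Starting from the 29th patient, the 12-month PFS rate will be re estimated for every 16 patients enrolled". Section 3.1 agrees that "the proportion of individuals randomized to each treatment group is dynamically" adjusted in the second stage. Neither section exempts the Stupp group or gives it a minimum share. Section 3.1 also gives the timing: "This study is expected to have an enrollment period of 24 months and a follow-up period of 24 months".

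**The concern.** Part (1) sizes the trial as if every arm ended with 50 patients. Part (2) guarantees equal arms for 28 of 210 patients (13%) and then lets the observed results decide.

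Stupp is the only control, so each experimental arm is compared with it. If the planning assumption is true and the experimental arms do better, adaptation on 12-month PFS moves patients away from Stupp. The comparator shrinks in exactly the scenario the trial is powered for, and all three comparisons lose precision together. If only one arm works, that arm grows and its power can exceed 80%. A reader of section 4 sees one arm size and one error rate and cannot tell which situation they describe.

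**Working it through.** **Inputs.** From section 4: 0.40 v 0.70 at 12 months, alpha 0.05, beta 0.20, 50 per group, 210 recruited, 7 per arm for the first 28, then blocks of 16. From section 3.1: 24 months of enrolment. The protocol does not say whether alpha is one- or two-sided; two-sided is assumed.

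**Step 1: reproduce the 50.** The mean proportion is 0.55.

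n = [1.96·√(2·0.55·0.45) + 0.8416·√(0.40·0.60 + 0.70·0.30)]² / 0.30² = (1.379 + 0.565)² / 0.09 = 41.97, so 42 per group.

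With continuity correction: (41.97/4)·[1 + √(1 + 4/(41.97·0.30))]² = 10.49 · 2.148² = 48.4, so 49 per group.

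The stated 50 is therefore the fixed, equal, two-group figure. Exact power at 50 v 50 is 0.876 (Pearson) or 0.829 (continuity-corrected). The total of 4 × 50 = 200 assumes four equal arms.

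**Step 2: when adaptation can take effect.** Accrual is 210/24 = 8.75 a month, so 12 × 8.75 = 105 patients, half the trial, enter before the first 12-month outcome is complete. If only completed outcomes count, allocation up to then is equal on average and Stupp has about 105/4 = 26 patients. If partial follow-up is used through a survival model, adaptation can act from patient 29.

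**Step 3: power when the control arm shrinks.** No allocation rule is needed for this. Exact power at 32 Stupp v 59 experimental is 0.80 (corrected 0.74), and at 20 v 63 it is 0.69 (0.59).

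**Step 4: simulate the scheme.** The set-up was 7 per arm for 28 patients, blocks of 16 up to 210, exponential PFS, no dropout and 2000 runs per setting. The final test was each arm against Stupp on 12-month PFS, two-sided 0.05, with no adjustment for three comparisons. Three weightings were assumed: the posterior probability of being best, P(best); its square root; and P(best) raised to the power n/2N. Two data sources were tried: (a) completed 12-month outcomes with a Beta(1,1) prior, and (b) an exponential-gamma posterior with censoring.

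Stupp at 40% and all three experimental arms at 70%:

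| Data | Weighting | Mean Stupp n | P(Stupp n ≥ 50) | Power, Pearson | Power, corrected |
|---|---|---|---|---|---|
| (a) | P(best) | 32.5 | 0.025 | 0.771 | 0.699 |
| (a) | square root | 35.9 | 0.042 | 0.823 | 0.758 |
| (a) | n/2N | 37.7 | 0.052 | 0.823 | 0.760 |
| (b) | P(best) | 16.0 | 0.005 | 0.567 | 0.438 |
| (b) | square root | 21.2 | 0.003 | 0.680 | 0.573 |
| (b) | n/2N | 26.2 | 0.004 | 0.763 | 0.682 |

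Pearson power with fewer effective arms:

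| Effective arms | (a) | (b) |
|---|---|---|
| Two | 82-86% | 67-84% |
| One | 90-91% | 86-92% |

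With one effective arm the corrected test gives 78-88% across (a) and (b). Over all 18 settings (three weightings, two data sources, three scenarios) Stupp reached 50 patients in at most 29% of trials.

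**Step 5: is adapting Stupp the cause?** With Stupp held at 25% and adaptation only among the experimental arms, Pearson power with three effective arms, in the same order of weightings, becomes 0.833, 0.852, 0.865 in (a) and 0.760, 0.819, 0.847 in (b). Most of the loss is recovered. The rest comes from unequal experimental arms.

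**The case against.** There are four serious points on the other side.

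- **The statistical analysis plan may hold the rule.** Weights, priors, a control floor and simulated operating characteristics are often placed there. That is fair, and their absence from the protocol is not the complaint. The protocol itself states an arm size and an error rate as the basis for recruiting 210 patients, and its own allocation section does not produce them. A control floor elsewhere could bring Stupp back to about 52, but the experimental arms would still vary, so 50 in each group at beta 0.20 would still not describe the design.
- **The closest reading shows a small loss.** Re-estimating the 12-month rate from observed data is nearest to (a). There Pearson power falls below 80% by at most 3 points, and only with three effective arms. This stands, and it limits the size of the concern. With the corrected test, the version that reproduces the 50, the figure is 70-76%.
- **The larger losses depend on a binary final test.** A log-rank test at the mean arm sizes in (b), under the same exponential model, gives 89% (16 v 64), 93% (21 v 63) and 95% (26 v 61). This also stands as arithmetic, with arm sizes held at their means. But section 4 sizes the trial on 12-month proportions, and a different test would need its own sample size statement.
- **The wording could mean all experimental patients pooled against Stupp.** Pearson power would then be 91-93% at 32-38 controls, and 69%, 78% and 85% at 16, 21 and 26. But 50 in each of four groups is not a pooled calculation, so this reading does not support the stated figure either.

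**Conclusion.** The concern holds. The arithmetic in section 4 is correct for a fixed equal two-group comparison, but the planned trial is not one. Neither 50 per group nor beta 0.20 describes it.

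The size of the error can only be given as a range. With all three experimental arms at 70%, power per comparison runs from about 57% to 82% (Pearson), depending mainly on whether partial follow-up feeds the adaptation. With one effective arm it is 86-92%. So the trial is not underpowered in every case; the stated power simply cannot be relied on. The range rests on assumed weightings, priors, exponential PFS, no dropout and unadjusted two-sided tests at 0.05. A milder rule would leave more Stupp patients and a smaller loss. The mismatch between the two parts of section 4 depends on none of these assumptions. It should be fixed.

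**What to change.** In section 4, replace the fixed figure with the expected size of each arm and the simulated power of the rule that will be used, under one, two and three effective arms. State whether completed 12-month outcomes or time-to-event data drive the adaptation, and which final test the power refers to.

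State also how the Stupp arm is protected. One option is to hold it at 25%, about 52 of 210, and adapt only among the three experimental arms; a minimum Stupp share is another. Holding 25% does not by itself secure 80% for every comparison (0.760 in one setting above), so the restated power must come from the simulation.

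The cost is two or three sentences and a simulation, best done before adaptation begins at patient 29. Protecting the control arm needs no extra patients. Its price is that, when all experimental arms are better, about 52 patients receive Stupp instead of about 16-38. If the chosen rule gives less than 80%, either the stated power comes down or N goes up.

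### Allocation is re-set on 12-month PFS from patient 29, when only about 2–3 progressions are expected over four arms (4–7 if first updated after patient 44) and no 12-month success is possible

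*Protocol*

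**What the plan says.** Section 4, part (2), sets an equal-allocation run-in: "Among the first 28 patients, an average of 7 were allocated to each group". It then fixes the quantity that drives allocation, the start and the interval: "Starting from the 29th patient, the 12-month PFS rate will be re estimated for every 16 patients enrolled". The stated purpose is "in order to improve trial efficiency". Section 3.1 describes the second stage in similar terms: "probability estimates are continuously updated based on the efficacy evaluation results of each group in the first stage".

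The wording leaves open whether the first update comes once the 28 run-in patients are enrolled or after a further 16 (patient 44). The protocol sets no minimum follow-up, event count or accrual pause before an update, and names no earlier outcome for updating.

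The size and pace of the trial are given in section 4 ("we plan to recruit 210 patients to ensure sufficient sample size for the final analysis") and section 3.1 ("This study is expected to have an enrollment period of 24 months and a follow-up period of 24 months").

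On the data available for updating, section 3.1 states "MRI enhanced scans will be performed every month during the follow-up period to observe PFS", and also "After stopping the study treatment, the subjects enter the follow-up period".

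**The concern.** A 12-month rate takes 12 months to observe. At the planned pace, half of the 210 patients are enrolled before the first patient can be known to be progression-free at 12 months. Early updates then rest either on failures alone or on a handful of progressions extrapolated to 12 months.

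The treatment schedule thins the data further. Under section 3.1 the two antibody arms receive the same treatment as Stupp until adjuvant therapy begins, 28 days after chemoradiotherapy. Most follow-up at the first update therefore says nothing about the antibodies.

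What is at stake is whether the early updates serve the efficiency aim. If allocation hardly moves, they do little. If it moves strongly, it moves largely by chance, and a poor arm may be favoured or a good one starved.

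**Working it through.** **Inputs.** From section 4: 210 patients, run-in of 28 (7 per arm), updates every 16, 12-month PFS 40% (Stupp) and 70% (experimental). From section 3.1: 24 months of enrolment; antibodies start 28 days after chemoradiotherapy. Assumed: uniform accrual, exponential PFS, and 6 weeks of radiotherapy (30 fractions, five a week).

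**The plan's own figure.** 40% v 70%, two-sided 5%, 80% power, with continuity correction, gives 49 per group, in line with the stated 50. Then 4 × 50 = 200 and 200 × 1.05 = 210.

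**Timing.** Accrual is 210/24 = 8.75 per month. Patient 28 enrols at 28/8.75 = 3.2 months and patient 44 at 44/8.75 = 5.0 months. The first patient enrols at 1/8.75 = 0.11 months and reaches 12 months of follow-up at month 12.11, when 12.11 × 8.75 = 106 patients are enrolled.

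**Expected progressions.** Monthly hazards are −ln(0.4)/12 = 0.0764 and −ln(0.7)/12 = 0.0297. Expected progressions are the sum over enrolled patients of 1 − exp(−hazard × follow-up), with equal allocation. The lower figure is for Stupp at 40% and three arms at 70%, the higher for all arms at 40%.

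| Enrolled | Month | Mean follow-up (months) | Patients with 12 months | Expected progressions, four arms |
|---|---|---|---|---|
| 28 | 3.2 | 1.5 | 0 | 1.7–3.05 |
| 44 | 5.0 | 2.5 | 0 | 4.1–7.3 |
| 60 | 6.9 | 3.4 | 0 | 7.5–13.1 |
| 76 | 8.7 | 4.3 | 0 | 11.7–20.2 |
| 92 | 10.5 | 5.2 | 0 | 16.8–28.5 |
| 108 | 12.3 | 6.1 | 3 | 22.5–37.8 |

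If the 210 patients took anything from 12 to 48 months to enrol, the ranges would be 0.9–5.7 progressions at patient 28 and 2.2–13.0 at patient 44, still with nobody at 12 months.

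**Reached the antibody phase.** 42 + 28 = 70 days after starting: 7 of 28 patients at the first reading, 23 of 44 at the second.

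**Precision in one arm at patient 28.** An arm has 7 patients and 7 × 1.54 = 10.8 patient-months. With an illustrative Gamma(1, 13.1) prior on the hazard, the posterior after d progressions is Gamma(1 + d, 23.9). The 95% interval for 12-month PFS is 16–99% with d = 0, 6–89% with d = 1 and 3–73% with d = 2. The prior alone gives 3–98%.

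**Ranking.** Trials were simulated with equal allocation, Stupp at 40% and the others at 70%, and arms ranked by posterior mean hazard. The lower figure takes constant hazards. The higher keeps the antibody arms at the Stupp hazard until day 70. Stupp, truly worst, ranks in the top two (50% by chance) in about:

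- 33–43% of trials at patient 28
- 20–35% at patient 44
- 14–27% at patient 60
- 8–20% at patient 76
- 4–14% at patient 92

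Repeat runs shift these by one or two points.

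**Patients affected.** Each update allocates the next 16 patients.

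- Resolved 12-month outcomes only: five updates (28 to 92) allocate 5 × 16 = 80 of 210 − 28 = 182, or 4 × 16 = 64 of 210 − 44 = 166 if updating starts at 44.
- Censored model: updates at 28, 44 and arguably 60 allocate 3 × 16 = 48 of 182 (26%), or 2 × 16 = 32 of 166 (19%).

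**The case against.** The strongest reply is that a Bayesian survival model with censoring uses partial follow-up, so 12 months is not the point at which information begins. The protocol does not exclude such a model, and the SAP may specify it. This stands in part. It makes the rate computable, and by patients 76 and 92 there are 12–28 expected events with misranking down to about 4–20%. It cannot supply events that have not occurred by patients 28 and 44.

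Two stronger readings are tempting. A reader might infer that the early updates carry no information at all, but 33–43% at patient 28 is better than 50%, and a small tilt that grows with the data is how adaptive randomisation is meant to work. A reader might also infer that 80 of 182 patients are allocated on inadequate data whatever the method. That holds only if updates count resolved 12-month outcomes, which the protocol does not say.

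Harm also depends on the formula. In illustrative runs with four equal arms, the mean highest and lowest allocation probabilities at a first update at patient 28 were 0.48 and 0.07 when proportional to the probability of being best, 0.37 and 0.13 with its square root, and 0.27 and 0.23 with a strongly damped exponent. A more informative prior would also damp early movement. Serious harm is therefore not shown. The reply does not rescue the start at patient 29, since weak damping follows noise and strong damping makes the first updates nearly idle.

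**Conclusion.** The point holds, and should be fixed. The protocol itself fixes the endpoint, start and interval, and at its own pace the first update has about 2–3 expected progressions over four arms (about 4–7 if it follows patient 44), with no 12-month success possible before about 106 patients.

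Its reach depends on the updating method, which is open: 80 of 182 patients (64 of 166) with resolved outcomes only, or about 48 of 182 (32 of 166) with a censored model. In the second case the information is little, not nil.

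The event counts assume uniform accrual and exponential PFS. A slower start to accrual lengthens early follow-up: under a quadratic ramp, 2.9–5.1 progressions are expected at patient 28 and there is still nobody at 12 months through patient 60. The intervals and rankings also depend on the illustrative prior. The documents do not allow the final damage to arm sizes or power to be stated, because formula and prior are not given.

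**What to change.** 1. Keep the 12-month PFS rate for the final analysis.
2. State that updates use all PFS follow-up with censoring, not only resolved 12-month cases.
3. Replace the start at patient 29 with 1:1:1:1 allocation until a pre-set minimum amount of information is reached, for example a pooled number of PFS events or a minimum follow-up. Choose the threshold by simulation together with the allocation formula, and say where the first update falls.
4. State that the monthly MRI also supplies PFS data during adjuvant treatment, or reconcile section 3.1, which ties it to a follow-up period entered after study treatment stops.

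Requiring 5 events in every arm is not advised as a fixed rule. In simulation it is met at a median of patient 92 if all arms are at 40%, but only at patient 124–140 of 210 under 40%/70%, which removes much of the adaptation the design is meant to provide. For scale, a pooled 12–20 events corresponds to about patient 76 under uniform accrual.

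The cost is protocol wording and a simulation. Adaptation starts later and fewer patients are redirected. A later start does not by itself prevent chance imbalance. In runs with equal arms and allocation by probability of being best, waiting for 5 events per arm moved the median smallest/largest final arm only from 24/86 to 31/79. With the damped exponent it moved from 38/68 to 40/66. The formula therefore has to be settled together with the start.

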5.3 Regulations on data management and data traceability

The designed CRF is in triplicate (carbonless), and the second copy of the CRF is submitted to the data management personnel participating in this clinical trial to establish a unified database. After completing at least 5 CRFs, the trial will be promptly submitted to the data administrator through clinical monitoring to establish the corresponding database. All data will be entered in duplicate using computer software to develop a data entry program.

During this period, the questionnaire will be forwarded to the researchers for data review through clinical monitors, and the researchers should answer and return it as soon as possible. The locked data file cannot be changed again. The database will be handed over to statistical analysts for statistical analysis according to the requirements of the statistical plan. Submit the statistical analysis report to the main researcher of this experiment to write the research report.

Provide training to researchers on relevant regulations and SOPs, and ensure that all researchers strictly comply with them to record truthfully, timely, accurately, and completely, prevent omissions and arbitrary modifications, and avoid forging or fabricating data; Inspectors strengthen the verification of various records. The follow-up medical records of the subjects should be kept together with the CRF as the original data. Each center's laboratory department provides participation in the quality control of the Ministry of Health's clinical laboratory center

The certificate of conformity shall be stored in the computer connected to the inspection equipment for at least three years for future reference.

5.4 data privacy

All records related to the identity of the subjects shall be kept confidential and shall not be disclosed to the public beyond the scope permitted by relevant laws and/or regulations.

6 , informed consent

Explanation on Informed Consent

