7.4 Criteria for determining the severity of adverse events

Refer to the grading standards for drug adverse events in NCI-CTCAE 5.0 version.

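### The 16-patient allocation update names only efficacy as its input, and no stated step compares toxicity between arms or leads to a decision to hold an arm during enrolment

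*Protocol*

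**What the plan says.** **Allocation.** The first 28 patients are split 7 per arm. After that, section 4 (2) states that "the 12-month PFS rate will be re estimated for every 16 patients enrolled, and subsequent randomization probabilities will be calculated based on observed data". Section 3.1 describes the same stage: "probability estimates are continuously updated based on the efficacy evaluation results of each group in the first stage". Neither place names a toxicity quantity.

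**Treatment.** Three of the four arms add to Stupp. In the PD-1/VEGF arm, "After completing synchronous radiotherapy and chemotherapy for 28 days, TMZ combined with PD-1/VEGF dual antibody will be used as adjuvant therapy"; the PD-1/CTLA-4 arm has the same structure. In the modified Stupp arm, "high-dose PGT 66Gy/30Gy will be given locally". Section 2.2 makes safety and the incidence of radiation necrosis secondary objectives.

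**Safety actions.** Section 3.3.3 covers the individual: if a subject is unsuitable or violates the protocol, "or for management and/or other safety reasons, the researcher may discontinue" that subject's treatment. Section 7.6 has each SAE reported to regulators, the ethics committee and the sponsor or applicant, and the researcher decides case by case whether to stop or reduce the drug.

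**Data available.** Severity is graded (section 7.4: "Refer to the grading standards for drug adverse events in NCI-CTCAE 5.0 version"), relatedness is judged (section 7.5), and case report forms (CRFs) move during the trial (section 5.3: "After completing at least 5 CRFs, the trial will be promptly submitted to the data administrator").

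**The concern.** The protocol fixes a recurring point at which allocation to each arm is recomputed, and it fixes what is looked at there. Serious non-fatal toxicity is not on that list. Judging single events for causality does not show that an arm's rate exceeds Stupp's, least of all for events that radiotherapy or TMZ also cause. A side-by-side count does. Without one, an excess in an intensified arm has to be noticed from a sequence of individual reports while enrolment to that arm continues.

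The point is limited to non-fatal toxicity. Death normally counts as a PFS event, so fatal toxicity would lower the arm's estimated rate. That is an assumption, because the protocol does not define PFS.

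Holding an arm is trial conduct and belongs beside the allocation rule, so this is not a detail that can be left to the SAP.

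**Working it through.** **1. The plan's own size.** Section 4 (1) gives 50 per group for 12-month PFS of 40% against 70%, alpha 0.05, power 80%. Two-sided, with pooled proportion 0.55:

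n = [1.96·√(2·0.55·0.45) + 0.842·√(0.24 + 0.21)]² / 0.30² ≈ 42 per arm, or 49 with continuity correction.

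The stated 50 is reproduced closely. The target after dropout is 210. With equal shares after the first 28, an arm enrols 7 + (210 − 28)/4 = 52.5 patients.

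**2. What enters the update.** Sections 3.1 and 4 (2) agree on efficacy. Sections 3.3.3 and 7.1 to 7.6 contain patient-level discontinuation, grading, causality and single-SAE reporting. None contains a comparison by arm or a decision about an arm.

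**3. When a by-arm check becomes possible.** The protocol says "This study is expected to have an enrollment period of 24 months". Assuming uniform accrual, that is 210/24 = 8.75 patients a month, so patient i enters at 24·i/210 months. Updates fall after patients 28, 44, …, 204, every 16/8.75 ≈ 1.8 months. Assume 6 weeks of radiotherapy, antibody start at week 10 (6 weeks plus 28 days), and a 2-month observation window.

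| Update after patient | Evaluable, antibody window (all arms) | Evaluable, boost window (all arms) | With 12 months of follow-up |
|---|---|---|---|
| 28 | 0 | 0 | 0 |
| 44 | 6 | 14 | 0 |
| 60 | 22 | 30 | 0 |
| 76 | 38 | 46 | 0 |

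Patient 60 is the first workable look, with 150 patients still to allocate. From 60 to 204 there are (204 − 60)/16 + 1 = 10 looks. Twelve-month follow-up is complete for nobody through patient 92, for 2 to 3 patients at 108 (depending on rounding) and for 19 at 124.

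**4. How often a trigger would fire.** All toxicity rates here are assumptions. The trigger is a posterior probability above 0.90 that the arm's rate exceeds concurrent Stupp by more than 10 points, with Beta(1,1) priors, at least 5 evaluable patients in each of the two arms, and equal shares. Results are by simulation.

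| Assumed true rates | Trigger fires |
|---|---|
| One antibody arm 50%, Stupp 20% | about 83% (34% by patient 76, 55% by 108, 68% by 140) |
| Boost arm 50%, Stupp 20% | about 85% |
| One antibody arm 40%, Stupp 20% | about 54% |
| All arms 20% | about 5% per arm, 14% for any arm |
| Three arms 30%, Stupp 20% | 46 to 47% for at least one |
| Both antibody arms 35%, Stupp 20% | 56 to 57% for at least one |

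Raising the cut-off to 0.95 lowers the 14% to about 6% and the 83% to about 72%.

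**5. Radiation necrosis.** With a 6-month window after radiotherapy, the first look with about 5 per arm is patient 92 (118 left). With 9 months it is patient 124 (86 left). At an assumed 25% against 5%, the boost arm is flagged in about 54% and 47% of trials.

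**6. What a flag could save.** At 50% against 20%, if every flag led to a lasting hold, mean enrolment in the arm falls from 52.5 to 31.1. That is (52.5 − 31.1)·0.30 ≈ 6 fewer patients with excess toxicity. If every arm reopened at the next update, mean enrolment is 49.1, and the saving is (52.5 − 49.1)·0.30 ≈ 1.

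**The case against.** Driving response-adaptive randomization by the efficacy endpoint is ordinary, and the two sections agree, so nothing in the quoted text is an error. Oversight exists: SAEs go quickly to regulators, the ethics committee and the sponsor, changes in intensity or relatedness must be updated, and one open-label team sees every arm. That team might well notice a 30-point excess unaided. A separate safety monitoring plan could exist, although the protocol mentions none. The size of the benefit rests wholly on assumed rates. All of this stands, and it is why the point is an improvement to consider and not a required correction.

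Section 4 (2) also speaks of observed data and prior knowledge in general terms and does not forbid other inputs. That is fair, but efficacy is the only input named.

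Three stronger readings are tempting and are not supported:

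- **That the adaptation steers patients towards a toxic arm.** Almost no 12-month data exist before patient 108, and the protocol does not say how incomplete follow-up enters the estimate. No early drift can be derived.
- **That the adaptive design creates the gap.** A fixed 1:1:1:1 trial without such a step would have the same one. The update is simply a convenient place to close it.
- **That a formula should set an arm's allocation to zero.** Added treatment may bring some expected toxicity. At 30% against 20% in all three arms, such a rule would stop at least one in 46 to 47% of trials, and a wrongly stopped arm would end with about 24 patients against the planned 50.

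**Conclusion.** The point holds in a limited form. As written, the protocol recomputes allocation every 16 patients on efficacy alone, and no stated step compares toxicity between arms or prompts a decision to hold one. Whether a non-fatal excess is acted on therefore depends on ad hoc judgement.

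This conclusion rests on the text and needs no assumed rate. The size of the gain does: uniform accrual over 24 months, equal shares, the chosen windows and the toxicity rates are all illustrative. Under them a by-arm check flags a large early excess in most trials, a moderate one in about half, and late necrosis in about half, with few patients left to protect by then. The gain is modest and the remedy inexpensive, so the change is worth considering.

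**What to change.** Add to section 4 (2), before each update issues new probabilities:

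- **Table by arm.** Grade 3 or higher AEs and SAEs related to any study treatment (radiotherapy, TMZ or antibody, so that Stupp is counted on the same basis), and radiation necrosis with its own longer window. Leave out progression and deaths from progression, since section 7.6 reports such deaths as SAEs. Count each arm and Stupp over the same time since entry.
- **Trigger for review.** For example, a posterior probability above 0.90 to 0.95 that the arm exceeds concurrent Stupp by a pre-set margin, with at least 5 evaluable patients in each. Choose the margin to allow for the toxicity expected from the added treatment.
- **Decision.** The principal investigator and ethics committee review promptly and decide whether to continue, hold or close the arm. Allocation is not changed automatically.

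**Cost.** An amendment with a short simulation to set margin, cut-off, minimum and windows; one table and one calculation at about 10 updates; and paper CRFs kept current for each. A statistician can hold the table so that the investigator sees by-arm interim safety data only when a trigger fires. Some reviews will be false alarms, at the rates shown in the working. No new committee is needed.
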